7.2.2.11. Disease Knowledge (Baseline and Post-intervention – Patient and Caregiver)

Disease Knowledge: A 14-item questionnaire assessing patients and caregivers' understanding of AML.

7.2.2.12. Information and Decision-Making Preferences (Baseline Only – Patient and Caregiver)

Information Preferences: A questionnaire assessing patient and caregiver preferences regarding treatment information.

Decision-Making Preferences: The Control Preference Scale assess patient and caregivers' preferred roles in treatment decisions.⁶⁴

7.2.2.13. Disease Understanding (Patient, Caregiver, and Physician)

Disease Understanding – Patient (baseline and post-intervention): A questionnaire assessing patient's prognostic understanding of illness and preferences regarding life expectancy discussions.

Disease Understanding – Caregiver (baseline and post-intervention): A questionnaire assessing caregiver's prognostic understanding of illness and preferences regarding life expectancy discussions.

Disease Understanding – Physician (post-intervention only): A physician-facing questionnaire assessing patient prognosis.

7.2.2.14 Decisional conflict and regret (post-intervention for decisional conflict and 1, 2, 3, and 6 month for decisional regret at)

Decisional conflict scale – A questionnaires that measures personal perceptions of uncertainty in choosing options, modifiable factors contributing to uncertainty, and effective decision making.⁶⁵

Decisional regret scale – A questionnaire that measures distress or remorse after a healthcare decision.⁶⁶

Was it worth it questionnaire – A questionnaires that assesses satisfaction with decision made.⁶⁷

7.2.2.15 Health-related quality of life (Post-Intervention and 1, 2, 3, and 6 month)

EQ-5D-5L: A health-related quality of life questionnaire that consists of five dimensions: mobility, self-care, usual activities, pain/discomfort, and anxiety/depression. Each dimension has 5 levels: no problems, slight problems, moderate problems, severe problems and extreme problems. The patient is asked to indicate his/her health state by ticking the box next to the most appropriate statement in each of the five dimensions. This decision results in a 1-digit number that expresses the level selected for that dimension. The digits for the five dimensions can be combined into a 5-digit number that describes the patient's health state.⁶⁸

7.2.2.16. Usability (Post-Intervention Only)

Usability questions – Patient and Oncologist: Questions to assess usability of the tool and/or summary.

7.2.2.17. Environmental Mastery (Baseline and Post-Intervention - Caregiver)

Ryff's Environmental Mastery: A 7-item questionnaire measuring whether the respondent makes effective use of opportunities and has a sense of mastery in managing environmental factors and activities, including managing everyday affairs and creating situations to benefit personal needs.⁷⁰

8.0 Data Handling and Statistical Considerations

8.1. Data Handling

8.1.1. The same protocols and procedures for data quality and control that are readily used for the NCI Community Oncology Research Program (NCORP) Research Base protocols currently being overseen by our office (which have accrued over 1,000 patients in the previous year) will be used for this study. Patients will fill out forms generated from RedCap and this information will be entered into RedCap (Section 9.5). Study personnel will perform SPPB and the scores will be entered into RedCap.

8.1.2. It is anticipated that allowing for the appropriate number of evaluable participants and by checking self-report measures for completeness, we will have a full complement of data. Every effort will be made to encourage and facilitate participants' completion of all questionnaires and all items on the questionnaires for each study assessment. In the event that missing data occur, every effort will be made to contact participants via phone and obtain the data or to find out why the questionnaires or items are missing. The reasons for missing data will be documented. Missing questionnaire items will be treated in accordance with the documented scoring procedures. Although it is very unlikely that missing values will not occur randomly, we will confirm their randomness. Multiple imputation⁷¹ will be applied to (1) give more accurate statistical tests and standard errors for key treatment effect parameters and to (2) give some indication of the sensitivity of the analyses to missing data. The causes and pattern of the missing data will be examined and taken into consideration in the design of future studies.

8.1.3. Data collected via the UR-GOAL communication tool will only be accessed by the following: 1) The research team and 2) The treating physician and their designee.

8.2. Data Analysis and Sample Size:

8.2.1. Analysis Plan for Aim 1

We anticipate thematic saturation will be reached with this number of participants (N=20) based on past similar research.^{43,44} We will conduct and audio-record all interviews, which will be transcribed by a professional transcription service. We will analyze the qualitative data using grounded theory and constant comparative methods, with coding to structure data into categories and create groups according to the broader issues or themes.⁷² An audit trail of the coding activity will be kept. We will critically examine the data collection and analysis process and reach consensus on key themes from patient feedback to be used to adapt the intervention in preparation for Aim 2.

8.2.2. Analysis Plan for Aim 2

We anticipate that our proposed sample size will be sufficient based on prior research⁷³ and also published guidance on usability study.^{74,75} The feasibility of the UR-GOAL tool

will be evaluated based on the percentage of patients consented to the study ultimately completing all study components.

Recruitment rate (percentage of patients who are approached and agree to enroll) will also be described. Other feasibility metrics include retention rate (percentage of patients who were enrolled and completed the intervention and assessments). The usability of the UR-GOAL tool will be evaluated using the SUS score.

We will consider the UR-GOAL study feasible if >50% of consented patients ultimately complete all study components. We chose 50% based on our prior behavioral intervention study in this population and published studies that utilize similar tools (e.g., value elicitation tool).^{73,76,77} We will use descriptive statistics to describe the measures. If we do not meet our usability and feasibility goals, we will further adapt the study and tool.

For other measures, these are being collected in preparation for a larger clinical trial in the future. As exploratory analyses, paired t-tests or McNemar's test will be used to evaluate change in measures from baseline to post-intervention. Linear mixed models will be used to assess change in measures over several time points.

Qualitative data from the semi-structured interviews will be analyzed as per Aim 1. Interviews will be conducted, audio-recorded, and transcribed. We will analyze the qualitative data using grounded theory and constant comparative methods, with coding to structure data into categories and create groups according to the broader issues or themes.⁷² An audit trail of the coding activity will be kept. We will critically examine the data collection and analysis process and reach consensus on key themes from patient feedback to be used to further adapt the tool.

For audio-recorded clinic encounters, we will use published shared decision-making coding schemes to assess quality of shared decision making.^{78,79} Coders will undergo extensive training and supervision by study investigators.

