3.2. Study Type

Aim 1: Qualitative study

Aim 2 and Exploratory Aim: Single-arm pilot study

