3.4. Inclusion and Exclusion Criteria for Patients

Inclusion criteria:

Aim 1

- Age ≥ 60 years (conventional definition of older age in AML)
- Established AML diagnosis (within 1 year)
- Able to provide informed consent
- English-speaking

Aim 2

- Age ≥ 60 years (conventional definition of older age in AML)
- Newly diagnosed AML
- Able to provide informed consent
- English-speaking

Exclusion criteria

- None

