3.11. Vulnerable Subjects

Recruitment will exclude vulnerable populations such as fetuses, neonates, children, pregnant woman, prisoners, and institutionalized individuals. We will also exclude adults who are deemed to not have decisional capacity and those who lost their consent capacity during the study period, as per their treating oncologist.

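### Section 8.1.2 presumes that missing data are random and promises to confirm it; observed data cannot do so, and the presumption is implausible for month 1–6 follow-up in newly diagnosed older AML

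*Combined protocol and SAP*

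**What the plan says.** Section 8.1.2 is the only missing-data text. It expects essentially complete data, and any gaps are to be followed up by phone. It then states: "Although it is very unlikely that missing values will not occur randomly, we will confirm their randomness". It names no test, threshold or reporting rule for this.

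Multiple imputation, specified only by a literature citation, has two purposes. One is to "give more accurate statistical tests and standard errors for key treatment effect parameters"; the other is to "give some indication of the sensitivity of the analyses to missing data". No non-random scenario is described, and no rule is given for values that would fall after a death.

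The section also contains real safeguards: "The reasons for missing data will be documented", and "The causes and pattern of the missing data will be examined and taken into consideration in the design of future studies".

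The setting comes from other sections. Section 3.2 reads "Aim 2 and Exploratory Aim: Single-arm pilot study". Section 3.4 requires age 60 or over and "Newly diagnosed AML" for Aim 2. Section 3.11 excludes "those who lost their consent capacity during the study period". Sections 7.1, 7.2.2.14, 7.2.2.15 and 9.1.2 schedule best-worst scaling (BWS), decisional regret and EQ-5D-5L at months 1, 2, 3 and 6. Section 8.2.2 analyses repeated measures with linear mixed models and does not state their missing-data assumption.

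**The concern.** The sentence makes two claims, and neither stands.

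The first is that non-random loss is very unlikely. In this cohort the obvious reasons for a missing month 3 or month 6 form are death, being too ill, or loss of capacity. All are tied to the health and attitudes that the forms measure.

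The second is that randomness can be verified. Lost and retained patients can be compared on what was recorded earlier, and that is useful. But missing at random and missing not at random differ only in how loss depends on values nobody has seen, so no such comparison can tell them apart.

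At stake are the month 1–6 results. BWS over time is the whole Exploratory Aim (Section 2.3), and Section 8.2.2 says the other measures are collected to prepare a larger trial. If health-related loss is treated as random, later health would tend to look too good and regret too low. A plan that does not exclude it also leaves room to impute quality of life or regret for patients who have died.

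**Working it through.** The plan gives no expected loss, no test and no power figure, so there is no figure of its own to reproduce. The calculations below are illustrative, with assumptions marked.

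**1. Is health-related loss plausible?** Section 1.1 cites 60-day mortality of 15–20%, for intensive chemotherapy only. Applied to all 15 Aim 2 patients as an upper-side input:
- Expected deaths by day 60: 15 × 0.15 = 2.25 to 15 × 0.20 = 3.0.
- Chance of at least one death: 1 − 0.85^15 = 0.913 to 1 − 0.80^15 = 0.965.

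Section 1.1 describes mortality on lower-intensity treatment as reduced and gives no figure. At an assumed 5–10%, the chance of at least one death is 1 − 0.95^15 = 0.537 to 1 − 0.90^15 = 0.794. No 6-month mortality is given.

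**2. How much could a baseline check see?** Assumed: two-sample t-test at two-sided 5%, true difference 1 SD, k patients missing and N − k observed. N is 15 (all alive) or 12 (3 deaths = 0.20 × 15). Power comes from the noncentral t with N − 2 degrees of freedom and noncentrality √[k(N − k)/N]. For N = 15 and k = 2 this is √(2 × 13/15) = 1.317, with critical value 2.160 and power 0.231.

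| k missing | Power, N = 15 | Power, N = 12 |
|---|---|---|
| 2 | 0.231 | 0.215 |
| 3 | 0.300 | 0.274 |
| 4 | 0.355 | 0.315 |
| 5 | 0.394 | 0.339 |

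The check misses a 1 SD difference between 1 − 0.394 = 61% and 1 − 0.215 = 79% of the time (rounded).

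**3. Does such a check target the right thing?** A simulation used 15 patients with one baseline and one follow-up value. Assumed: correlation 0.3–0.7, 20% or 40% missing, and log-odds of loss rising 1.5 per SD of worse value. A baseline t-test rejected in 44–57% of simulated studies when loss depended on the observed baseline. It rejected in only 8–28% when loss depended on the unseen follow-up value, against about 5% under completely random loss. So it is least sensitive to the mechanism that matters most. Prediction from baseline, standing in for imputation under missing at random, stayed biased by 0.11–0.40 SD in the non-random case and by at most about 0.02 SD when loss was truly at random.

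**4. How far could a mean move?** Assume the k living patients with missing values are 1 SD worse than a missing-at-random analysis predicts. The mean among patients alive then shifts by k/N SD:
- N = 15: 2/15 = 0.13 to 5/15 = 0.33 SD.
- N = 12: 2/12 = 0.17 to 5/12 = 0.42 SD.

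Against the standard error of the observed mean, 1/√(N − k) SD, the ratios are:
- N = 15: 0.133/0.277 = 0.48 to 0.333/0.316 = 1.05.
- N = 12: 0.167/0.316 = 0.53 to 0.417/0.378 = 1.10.

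This applies only to directional scales. BWS rankings have no worse direction.

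**5. What is not affected?** The feasibility rule in Section 8.2.2 counts consented patients who complete everything. Non-completers count against it directly, without imputation. The 1–2 week measures leave little time for loss.

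**The case against.** The strongest case against concerns weight. This is a small single-arm pilot, the affected tests are labelled exploratory, and its only numeric success rule does not depend on imputed values. That stands and limits the point to the exploratory longitudinal results.

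Second, the sentence follows one on missing questionnaire items and may have been written with sporadic gaps in mind; confirming randomness could then mean reviewing the documented reasons. This is a fair reading of intent. But no other text covers missed visits, and a review of reasons cannot establish randomness either. The stated use of the examination of causes is future study design, not this analysis.

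Third, the imputation method rests on a cited source, which may cover more than the visible text does. So the claim can only be that the plan itself states no non-random scenario and no rule for values after death.

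Fourth, the figures rest on assumed inputs, and the standard error is that of a single-visit mean, not of a change from the mixed model. That also stands. The logical point does not depend on them.

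A reader might infer that the plan commits to declaring randomness confirmed whenever a test is non-significant. It does not: no test or reporting rule is named, so this is a risk that the wording invites. Nor does the reference to treatment effects, which sits oddly in a single-arm study, show an analysis error. It is clerical.

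**Conclusion.** The concern holds for the presumption and the promise. Both are stated, and both are wrong as written: randomness cannot be confirmed from observed data, and presuming it conflicts with the protocol's own population, follow-up length, cited early mortality and capacity exclusion. The absence of a rule for values after death is a real gap in the visible text.

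The size is modest. Under the assumptions above, a baseline check has 21–39% power for a 1 SD difference. A health-related loss of 2–5 living patients could move a directional mean by 0.13–0.42 SD, or about 0.5–1.1 standard errors. These figures show scale and do not predict what will happen in this trial.

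The effect is confined to the exploratory month 1–6 results. A reader might infer that the feasibility conclusion is in doubt; it is not, because the >50% rule is a completion count. The change should be made because it is cheap and these results feed a larger trial.

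**What to change.** In Sections 8.1.2 and 8.2.2:

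- Delete the presumption and the promise to confirm randomness. Refer to change over time instead of treatment effects.
- Keep the linear mixed model and state missing at random as a working assumption that the data cannot test.
- State that values after death are not imputed.
- Report month 1–6 results among patients alive. At each visit, give the numbers dead, too ill or without capacity, and withdrawn, from the reasons already being documented.
- For BWS, report completers at each visit. Compare descriptively the baseline rankings (the tool is completed at baseline, Section 5.4) of patients later lost and those retained.
- Give the stated sensitivity purpose some content: a simple delta-shift, in the worse direction, for living patients with missing decisional regret scores. Section 7.2.2.15 describes EQ-5D-5L only as a five-digit profile, which cannot be shifted as it stands. Include it only if a numeric score is specified first; otherwise describe it.

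The cost is wording and a little extra analysis, with no new data collection. Completeness will look less favourable, results among patients alive describe survivors only, and the delta is itself an assumption in about 15 patients.

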9.0. Data Management

9.1. Data Collection Table

9.1.1. Aim 1

	Eligibility and Consent Form	Assessment
Informed Consent	X	
Demographics		X
Clinical and Cancer Characteristics		X
Qualitative Interview		X
Short Physical Performance Battery/Virtual Short Physical Performance Battery, Activities of Daily Living, Instrumental Activities of Daily Living, Fall History		X
Nutritional Status		X
Comorbidity		X
Geriatric Depression Scale-15 (GDS-15), Generalized Anxiety Disorder-7 (GAD-7)		X
Social Support		X
Medications		X
Mini-Cog		X
Information and Decision-Making Preferences		X
Disease Understanding - Patient		X

9.1.2. Aim 2

a) Patients

	SCHEDULE OF DATA COLLECTION			
	Eligibility and Consent Form	Baseline Assessment (week 0)	Post-intervention Assessment (week 1-2)	Month 1, 2, 3, and 6
Informed Consent	X			
Demographics		X		
Clinical and Cancer Characteristics		X		
Qualitative Interview			X	
Short Physical Performance Battery/Virtual Short Physical Performance Battery, Activities of Daily Living, Instrumental Activities of Daily Living, Fall History		X		
Nutritional Status		X		
Comorbidity		X		
Geriatric Depression Scale-15 (GDS-15), Generalized Anxiety Disorder-7 (GAD-7)		X	X	
Social Support		X		
Medications		X		
Mini-Cog		X		
Perceived Efficacy in Patient-Physician Interactions (PEPPI)		X	X	
Patient-Centered Communication in Cancer Care (PCC-Ca-36)			X	
Shared Decision-Making (SDM-Q-9) ^a			X	
CollaboRATE Measure			X	
Preparation for Decision Making Scale			X	
Patient Disease Knowledge		X	X	
Information and Decision-Making Preferences - Patient		X		
Disease Understanding - Patient		X	X	
Decisional Conflict Scale			X	
Decisional Regret Scale and Was it Worth It Questionnaire				X
BWS component only of the tool				X
EQ-5D-5L			X	X
Usability (Usability questions)			X	

b) Caregivers

	SCHEDULE OF DATA COLLECTION		
	Eligibility and Consent Form	Baseline Assessment (week 0)	Post-intervention Assessment (week 1-2)
Informed Consent	X		
Demographics		X	
Qualitative Interview			X
Comorbidity		X	
Patient Health Questionnaire-2 (PHQ-2), Generalized Anxiety Disorder-7 (GAD-7)		X	X
Perceived Efficacy in Caregiver-Physician Interactions (PECPI)		X	X
Patient-Centered Communication in Cancer Care (PCC-Ca-6) – adapted caregiver version			X
Ryff's Environmental Mastery		X	X
CollaboRATE Measure			X
Preparation for Decision Making Scale			X
Caregiver Disease Knowledge		X	X
Information and Decision-Making Preferences – Caregiver		X	
Disease Understanding – Caregiver		X	X

c) Oncologists

	SCHEDULE OF DATA COLLECTION		
	Eligibility and Consent Form	Baseline Assessment (week 0)	Post-intervention Assessment (week 1-2)
Informed Consent	X		
Demographics		X	
Shared Decision-Making (SQM-Q-Doc, physician version)			X
Disease Understanding – Physician			X

Usability questions			X
Qualitative Interview			After at least 1 patient per oncologist completed study procedures, can be done at any point during the study

9.2. All hardcopy research records will be stored onsite in the URMC, in locked research files at the WCI. The Cancer Center is secured with electronic key cards. Offices within the Cancer Center are again secured by key and data is kept in locked file cabinets. Electronic research records are stored on the URMC's password secured and firewall protected networks. These are the same methods of security used for patient medical records. For audio-recordings, these will be uploaded to Box within a week of the interview and deleted from the audio-recorded. All study data will be kept for a period of 7 years after the study and all reports and publications are complete.

9.3. All data collected for the current study will be used in post hoc analyses as appropriate. Data will not be used for future studies without prior consent of the patient. The patient's individual research record will not be shared with their treating physician, unless they provide consent or the patient's treating physician is a study physician, in which case they will have access to study data as a study co-investigator. Overall study results will be presented to participants, faculty and staff at the URMC after completion of the study. Study results will be presented at professional meetings and published.

9.4. The study coordinator will assign a numerical study ID to each participant once they have signed the consent form (chronologically based on the data they signed consent i.e., 001, 002, 003...). All study forms and questionnaires will use this number and the participant's first, middle, and last initials as identifiers, to ensure data integrity. Other identifying information will not exist on these forms. A complete list of study participants with study ID, name, and contact information will be maintained separately. This linkage information will only be accessible to the study coordinator, study investigators, and the individuals responsible for maintaining the database.

9.5. Additionally, data on the socio-demographics, clinical, and cancer and treatment characteristics will be collected and managed by the research teams at URMC using REDCap electronic data capture tools hosted at URMC.⁸⁰ We will also evaluate the medical records for clinical characteristics and outcomes, and utilize REDCap to collect and manage this information.

9.5a. URMC provides the following information on the **REDCap program**: "Vanderbilt University, in collaboration with a consortium of institutional partners, has developed a software toolset and workflow methodology for electronic collection and management of research and clinical trial data, called REDCap (Research Electronic Data Capture). The REDCap system is a secure, web-based application that is flexible enough to be used for a

variety of types of research. It provides an intuitive interface for users to enter data and real time validation rules (with automated data type and range checks) at the time of data entry. REDCap offers easy data manipulation with audit trails and functionality for reporting, monitoring and querying patient records, as well as an automated export mechanism to common statistical packages (SPSS, SAS, Stata, R/S-Plus). Through the REDCap Consortium, Vanderbilt has disseminated REDCap for use around the world. Currently, over 240 academic and non-profit consortium partners on six continents with over 26,000 research end-users use REDCap.⁸¹

9.5b. According to the Clinical and Translational Science Institute (CTSI), REDCap is supported with the following means. “The *CTSI Informatics Core*, a unit of the SMD *Academic Information Technology (AIT) Group*, will serve as a central facilitator for data processing and management. REDCap data collection projects rely on a thorough study-specific data dictionary defined in an iterative self-documenting process by all members of the research team, with planning assistance from the *AIT-CTSI Informatics Core*. The iterative development and testing process results in a well-planned data collection strategy for individual studies.”⁷²

9.5c. The CTSI states that regarding security, “REDCap servers are housed in a local data center at the University of Rochester and all web-based information transmission is encrypted. REDCap was developed in a manner consistent with HIPAA security requirements and is recommended to University of Rochester researchers by the URMC Research Privacy Officer and Office for Human Subject Protection.⁸¹

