7.2.3. Measures

Measures will be collected via the UR-GOAL tool, done in person, or mailed to the participants.

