7.2.2.9. Patient-Centered Communication (Post-Intervention Only – Patient and Caregiver)

Patient-Centered Communication in Cancer Care (PCC-Ca-36): A questionnaire assessing patient-centered communication in six domains: exchanging information, making decisions, fostering healing relationships, enabling patient self-management, managing uncertainty, and responding to emotions.⁵⁹ We will adapt the PCC-Ca-6 for caregivers.

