7.2.2.10. Shared Decision-Making (Post-Intervention Only – Patient, Caregiver, and Physician)

Shared Decision-Making Questionnaire (SDM-Q-9): A 9-item reliable questionnaire assessing patient satisfaction with the medical decision-making process.⁶⁰

Shared Decision-Making Questionnaire (SDM-Q-Doc): A 9-item reliable questionnaire assessing physician satisfaction with the medical decision-making process.⁶¹

CollaboRATE Measure: A 3-item questionnaire assessing patient, caregiver, and

physician shared decision-making.⁶²

Preparation for Decision Making Scale: A 10-item questionnaire assessing patients' and caregivers' perception of how useful the communication tool is in preparing them to communicate with their physician at a consultation focused on making a health decision.⁶³

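### Section 9.3 lets a treating oncologist who is a co-investigator see patients' post-visit ratings of that oncologist's own encounter, which risks favourable answers on exploratory scores

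*Combined protocol and SAP*

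**What the plan says.** Three access rules bear on this point.

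- **Section 9.3** starts from a prohibition: "The patient's individual research record will not be shared with their treating physician, unless they provide consent". It then adds a second exception, where the patient's treating "physician is a study physician, in which case they will have access to study data as a study co-investigator". The exception names no item that stays closed and no date before which access is barred.
- **Section 9.4** puts the participant's initials on all forms and says of the list joining study ID to name: "This linkage information will only be accessible to the study coordinator, study investigators, and the individuals responsible for maintaining the database".
- **Section 8.1.3** says that data collected through the tool "will only be accessed by the following: 1) The research team and 2) The treating physician and their designee". None of the conditions in 9.3 is repeated there. Section 7.2.3 says: "Measures will be collected via the UR-GOAL tool, done in person, or mailed to the participants".

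The measures concerned are post-intervention only. SDM-Q-9 is described as "A 9-item reliable questionnaire assessing patient satisfaction with the medical decision-making process" (7.2.2.10), and PCC-Ca-36 as "A questionnaire assessing patient-centered communication in six domains" (7.2.2.9). CollaboRATE covers shared decision-making. Under 9.1.2, caregivers complete CollaboRATE and an adapted PCC-Ca-6. The oncologist completes SDM-Q-Doc within 1-2 weeks of the same encounter (4.1.4 and 9.1.2).

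**The concern.** These scales ask patients and caregivers about an encounter with an oncologist on whom the patient depends at the start of AML care. If respondents believe that this oncologist can read their individual answers, some may answer more kindly than they otherwise would. Aim 2 has a single arm, and these scales have no baseline value, so neither a comparator nor a change score would remove such a shift.

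There is also an ordering problem. Nothing stops a co-investigator from reading the patient's SDM-Q-9 before completing SDM-Q-Doc on the same visit. The physician's rating could then no longer be taken as independent of the patient's.

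What is at stake is the level of these scores as carried forward. Section 8.2.2 says that the other measures are collected to prepare a larger trial, and section 1.6 plans to assess later whether the tool improves shared decision-making and communication.

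**Working it through.** No sample size, power or error-rate figure bears on this point. The check sets the sections side by side.

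1. **Does 9.3 open the ratings to the rated physician?** Yes, for one group. The default is no sharing. A treating physician who is a study physician is exempt, and the exemption covers study data without a carve-out. Post-visit ratings are study data.

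2. **Is the overlap of roles foreseen?** Yes. Section 9.3 provides for it. Section 4.1 also has a treating physician/study investigator presenting the study and taking consent, although the slash may mean either person. How many treating oncologists are co-investigators is not stated.

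3. **Could a co-investigator recognise his or her own patients?** Yes. Section 9.4 gives study investigators the link to names. Even without it, section 3.7 plans 15 patients and between 3 and 15 oncologists, so the average number of patients per oncologist is:
 - most: 15 / 3 = 5
 - fewest: 15 / 15 = 1

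 With 1 to 5 patients each, removing names would give little masking.

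4. **Is there a route for treating physicians who are not investigators?** Possibly. Section 8.1.3 opens tool-collected data to any treating physician, and 7.2.3 lists the tool as one of three ways to collect measures. Against this, section 6 lists the tool's components as best-worst scaling, fitness and prognostic awareness, none of which is a post-visit rating. Section 8.1.1 has patients complete REDCap forms. The route is left open by the wording but is not shown to be used.

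5. **Which outcomes are exposed?**

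| Outcome | Patient or caregiver rating of the encounter? | Exposed? |
|---|---|---|
| SDM-Q-9, CollaboRATE, PCC-Ca-36 (patient) | Yes | Yes |
| CollaboRATE, adapted PCC-Ca-6 (caregiver) | Yes | Yes |
| SDM-Q-Doc | No, physician's own rating | Only through seeing the patient's rating first |
| PEPPI | No, patient's self-efficacy | No |
| Coded audio recordings (8.2.2) | No, trained coders | No |
| Completion >50% (8.2.2) | No | No |
| SUS (8.2.2) | No, rates the tool | No |

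6. **Can the shift be sized?** No. The documents give no mean, standard deviation or effect of disclosure for these scales.

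**The case against.** The strongest reply is that the default in 9.3 already protects the record, and that access after a form is completed cannot change an answer already given. Bias needs respondents to know or suspect the access when they answer. The consent pages are not among the material reviewed, so what participants are told is unknown and cannot be counted as a gap. All of this stands, and it makes the problem a risk rather than a demonstrated bias. It does not remove the exemption, which is explicit. A patient whose own oncologist took consent under 4.1 has some reason to suspect access.

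A reader might infer more than the documents support in four respects:

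- **That the scores are biased upwards.** The direction is plausible, but neither its occurrence nor its size is established.
- **That all 15 patients' ratings are open to their oncologists.** This would require every treating oncologist to be a co-investigator or every rating to be entered in the tool. Sections 6 and 8.1.1 point away from the second.
- **That the interviews are ratings of the oncologist.** Section 2.5 has them explore the usefulness of the tool and barriers and facilitators to it. Section 8.2.2 uses the resulting themes to adapt the tool further.
- **That every shared-decision outcome is affected.** The recordings are coded by trained coders and do not depend on patient answers.

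It is also fair that 8.2.2 plans no patient-physician agreement analysis. The SDM-Q-Doc ordering matters only if the two ratings are later compared or read as independent.

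**Conclusion.** The point holds in limited form. An explicit rule in 9.3 allows a co-investigator oncologist to see identifiable patient and caregiver ratings of his or her own encounter, with no stated masking or delay. Section 8.1.3 is not reconciled with 9.3 and leaves a weaker route open for other treating physicians.

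The consequence is an avoidable risk of favourable responding, of unknown size, together with possible loss of independence of SDM-Q-Doc. It reaches the patients of co-investigators and their caregivers. The ceiling is the 15 planned Aim 2 patients, but the actual number cannot be derived. The conclusion assumes that some treating oncologists are co-investigators and that some respondents know or suspect the access.

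The feasibility and usability conclusions do not depend on these scores. The harm is confined to exploratory estimates that inform the planned larger trial. The change is worth making because it is cheap and can protect only ratings not yet collected.

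**What to change.** 1. Reconcile 8.1.3 with 9.3 so that treating-physician access covers only the UR-GOAL summaries (best-worst scaling, fitness, prognostic awareness), which the oncologist needs as part of the intervention.
2. In 9.3, state that patient and caregiver post-visit ratings are withheld from the rated oncologist, including a co-investigator, at least until that oncologist's SDM-Q-Doc is complete and data collection has ended. Apply the same limit to the linked identifiers for those ratings in 9.4.
3. State that these ratings are kept in REDCap, in line with 8.1.1, and not entered through the tool.
4. Tell participants, before they answer, that their oncologist will not see their individual ratings during the study.

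The cost is a few sentences in the protocol, a REDCap user-rights setting and one line in the survey introduction. The small downside is that a co-investigator cannot view his or her own patients' identifiable ratings until data collection ends. Interview transcripts need not be restricted, so the consensus review of themes in 8.2.2 can go on as planned.
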